Testing Financial Incentive Interventions in Dyadic-Smoker Couples

NCT04832360

Document Date: April 13, 2024

METHODS

Participants and Recruitment

As participation in the study was conducted virtually (e.g., over video teleconference and electronic survey), we utilized a Nationwide recruiting strategy to reach smokers across the contiguous United States. We recruited from three primary sources: Facebook/Instagram advertisements, Craigslist advertisements, and the ResearchMatch database of individuals interested in participating in health research studies. Both Facebook and ResearchMatch recruitment allowed for nationwide placement of recruiting messages. On Craigslist, we placed 134 advertisements in distinct geographic regions, targeting all 48 contiguous states at some point during the study. Each advertisement ran for 28 days.

We enrolled 95 dual-smoker couples (total N=190) from February 2021 to May 2022, consistent with recommendations to recruit ~30 participants per treatment arm for quantitative-focused feasibility studies²⁷. Prior to data collection, we had identified that an intent-to-treat sample of ~95 targets would allow us power of ~82% to compare the control and PIF conditions; estimates were power were based on prior research and past research on financial incentive treatments for smoking.^{21,28} Eligibility requirements were a) smoking ≥ 5 cigarettes daily, b) 18+ years of age, c) romantically partnered and cohabiting with another eligible participant. Individuals with psychosis risk, recent hospitalization, or current pregnancy were not eligible. Motivation or readiness to quit smoking was not a study prerequisite. Figure 1 shows the CONSORT diagram of enrollment; Table 1 shows the characteristics of enrolled participants. The first member of the couple to make contact with the research team was labeled the target; the other member was labeled the partner.

Overview of Procedures

The study consisted of a) a baseline video conference with surveys and biochemical verification of smoking, b) ten weeks of brief surveys, c) four weeks of optional online psychoeducation, and d) a 3-month follow-up video conference with surveys.

Baseline

Prior to the baseline video conference, both members of the couple completed surveys assessing smoking history, relationship quality, and smoking variables. Between the completion of these surveys and the video conference, randomization via a random number generator occurred. During the video conference, each person confirmed consent and used an IcoQuit Smokerlyzer to collect expired CO. Next, research staff explained procedures to participants, including the administration of experimental conditions. Dyads were randomly assigned via a random number generator to either a) No-FIT control, b) PIF-ST, or c) PIF-DT. In PIF conditions, either the target (PIF-ST) or both members (PIF-DT) were offered compensation of \$100 for completing the psychoeducation training and \$100 for being quit at follow-up. Participants could receive either or both incentives; partners could earn different amounts of incentives. Randomization was supplemented with stratification, resulting in slightly different sample sizes across condition. We stratified couples based on a) target gender, b) target smoking heaviness (<20 cigarettes per day, 20+ cigarettes per day), and 3) same- of different- sex couple status.

Treatment as usual

All participants received weekly links to a four-module (~ 1 hour weekly) online psychoeducation program combining behavioral change coaching with information about addiction and quitting. The program began one week after baseline; participants could access

links at any time during the study. Participants were also offered home delivery of NRT (patch and/or gum) calibrated to their quantity of smoking (patches) or time to first cigarette (gum).

Weekly surveys

Participants received weekly emails (if necessary, they received a follow-up reminder within three days) in which they engaged in a Timeline Follow-back (TLFB; Harris et al., 2009) to report if they had smoked cigarettes and/or used NRT in the past eight days (today + each day of the prior week). On average, participants completed 8.42 surveys.

Follow up

As with baseline, participants completed surveys at follow-up. Participants received bonus compensation for attending a video session; all participants who indicated abstinence in the survey were required to hold the video session to complete a breath test before receiving abstinence incentives. Participants were instructed not to vape within 24 hours of the breath test.

Measures

The primary outcomes were: 1) Feasibility, defined as percentage of targets retained at follow-up, aiming for >80%; and 2) Tolerability, defined from 8 items assessing the accessibility, benefits, and costs of the study scored on a 1(strongly disagree) to 7(strongly agree) scale. Participants also completed five open-ended questions on their experiences. The four secondary outcomes were: 1) Program completion, defined as completing all four psychoeducation modules; 2) Quit attempts (i.e., self-reported duration of greater than 24 hours without smoking), assessed via weekly surveys; 3) Point prevalence abstinence, defined as a) self-reported abstinence for 7+ days and b) expired CO collected via ICOquit breath sensors (≤ 5 ppm30); and 4) Joint abstinence, defined as both couple members being abstinent at follow-up.

Data Analysis

The primary outcomes were feasibility and tolerability in targets. The secondary outcomes were preliminary intervention effects among targets, with partners' outcomes as further descriptive dependent variables. Thus, for each analysis, we report outcomes separately by target and partner, with the exception of joint abstinence which was defined at the dyad-level. Results presented in Table 2 and Figure 2 thus show results separately for targets and partners. Student *t*, one-way ANOVA, ANOVA contrast tests, and Chi Square tests were used for analyses. For each analysis, we provide descriptive information as well as comparisons across conditions. When evaluating intervention outcomes, we focused our tests of significance on the PIF conditions combined compared to the no-FIT control. We provide descriptive follow-up tests comparing PIF-ST and PIF-DT, but note these tests necessarily involve larger confidence intervals and should be interpreted cautiously in a pilot trial. Data analysts were not blind to condition; two researchers verified the data and results. For retention rate and all preliminary efficacy outcomes, we utilized an intent-to-treat sample such that all participants' data were included in analyses. For the tolerability ratings, we report only participants who completed follow-up.

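### Should quit attempts, recorded only in the ten weeks of surveys, be tied to abstinence at the 3-month follow-up?

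*Combined protocol and SAP*

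**What the plan says.** The Measures section defines the second of four secondary outcomes as "Quit attempts (i.e., self-reported duration of greater than 24 hours without smoking), assessed via weekly surveys". No start or end of the counting period is attached. The third is "Point prevalence abstinence, defined as a) self-reported abstinence for 7+ days and b) expired CO collected via ICOquit breath sensors", with a limit of 5 ppm.

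The timing is found elsewhere. Overview of Procedures lists, after baseline, "b) ten weeks of brief surveys, c) four weeks of optional online psychoeducation, and d) a 3-month follow-up video conference with surveys". Weekly surveys gives each survey an eight-day look-back ending on the day it is filled in, notes that "if necessary, they received a follow-up reminder within three days", and reports a mean of 8.42 surveys completed. Follow up says "As with baseline, participants completed surveys at follow-up" without listing their content, and adds that "all participants who indicated abstinence in the survey were required to hold the video session to complete a breath test before receiving abstinence incentives". Baseline states that the PIF conditions carried \$100 "for being quit at follow-up": for the target in PIF-ST, and for both members in PIF-DT.

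Data Analysis puts the significance tests on the two PIF conditions combined against the control. It does not say how quit attempts and abstinence relate, or whether the follow-up surveys feed the quit-attempt outcome.

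**The concern.** Anyone smoke-free for seven days has gone more than 24 hours without smoking, so every verified abstainer has in substance made a quit attempt. The two outcomes come from different instruments, however, and the surveys stop before the follow-up. Someone who first stops in between could be scored as abstinent with no attempt on record. A reader would then not know whether a negative entry means that no attempt was made or that none was observed.

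The stake is the PIF-versus-control comparison. The uncovered days lead up to the visit at which PIF targets and PIF-DT partners, but not controls, can earn \$100 for having quit. If that prompted late stopping, attempts would be undercounted more in the PIF conditions than in the control.

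**Working it through.** The documents give no figure to reproduce on this point; the stated power of about 82% does not bear on it. The check is calendar arithmetic.

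**Inputs from the documents:** ten weeks of weekly surveys; a look-back ending on the completion day; a reminder within three days; follow-up at 3 months; at least 7 smoke-free days for abstinence; more than 24 hours for a quit attempt.

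**Assumptions, not in the documents:** ten surveys were expected, one per week; the first falls on day 7 or day 14; the last is completed 0 to 3 days after it is sent; the 3 months run from baseline, so follow-up is on day 84 or day 91.

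**Condition.** Let L be the day the last survey is completed and F the follow-up day.

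- L = first survey day + 9 × 7 + delay.
- Seven smoke-free days before the visit require a first smoke-free day no later than F − 7.
- A person whose first smoke-free day is L will usually not have passed 24 hours when filling in that survey, so day L counts as unrecorded.
- Unrecorded first smoke-free days therefore run from L to F − 7. Their number is F − L − 6, or zero if that is negative. At least one exists when F − L ≥ 7.

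| First survey (day) | F (day) | L, delay 0 / 3 | F − L, delay 0 / 3 | Unrecorded start days, delay 0 / 3 |
|---|---|---|---|---|
| 7 | 84 | 70 / 73 | 14 / 11 | 8 / 5 |
| 7 | 91 | 70 / 73 | 21 / 18 | 15 / 12 |
| 14 | 84 | 77 / 80 | 7 / 4 | 1 / 0 |
| 14 | 91 | 77 / 80 | 14 / 11 | 8 / 5 |

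In the third row, delays of 1 and 2 days give F − L = 6 and 5, so no start days.

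**Sensitivity to the anchor.** The documents do not say where the 3 months start. If follow-up came 91 days after the last survey, there would be 91 − 6 = 85 start days. The table is illustrative and does not bound the gap.

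**Missed surveys.** With ten expected, 10 − 8.42 = 1.58 (15.8%) were missed on average. Adjacent look-backs share one day, so a missed mid-period survey loses 8 − 2 = 6 days and a missed last survey loses 7. Without the tenth survey, L moves back 7 days; the third row becomes F − L = 14 / 11, with 8 / 5 start days. Missed surveys can thus produce the same mismatch on every schedule in the table.

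**What this shows.** The mismatch is possible. The table counts calendar dates, not people, and nothing in the documents converts one into the other. A late quitter with an earlier attempt on record does not create a mismatch.

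**The passages side by side.** Measures ties the outcome to the weekly surveys. Overview of Procedures runs those for ten weeks and lists the follow-up as a separate component. Weekly surveys and Follow up have separate headings. Together these say that quit attempts are those reported in the weekly surveys.

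**The case for a change.** The strongest case for acting is that little is asked: name the period, count by arm the verified abstainers without a recorded attempt, and add one sensitivity analysis crediting them with an attempt. The data are held, and the intention-to-treat statement does not help, because including everyone does not supply days that no survey covered.

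What stands is that the mismatch is possible, that the definition does not repeat its period, and that a difference between arms cannot be excluded.

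The rest is weaker. The incentive was explained at baseline and applied throughout the survey weeks; nothing in the documents suggests that stopping was concentrated after the last survey. The count would not isolate the cause, since missed surveys give the same pattern. The sensitivity analysis has its own faults:

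- It depends on attending a breath test that unlocks a payment offered only in the PIF conditions.
- It makes the quit-attempt outcome partly contain the abstinence outcome.
- It still misses short late attempts that ended in relapse.
- It would be chosen after the fact by analysts who know the allocation.

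It would exchange a possible arm-related undercount for a possible arm-related overcount.

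**Conclusion.** No change to the plan is needed. An analyst following the text would count quit attempts reported in completed weekly surveys, which is a sound outcome for that period. Abstinence is a status at one later time, and nothing requires the two to share a window. A participant who stops late and is verified is not lost, because abstinence captures that result. The unstated label is detail that the other sections supply; the added analysis is at best a trade-off with no clear gain.

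The possible effect is confined to one secondary outcome of a pilot. Feasibility, tolerability, program completion, abstinence and joint abstinence are untouched. Under the assumed baseline-anchored calendars, 0 to 15 start dates could give a verified abstainer without a recorded attempt; a later anchor or missed surveys would widen that. The number of participants concerned, and the direction of any bias, cannot be obtained from the documents, and the number may be zero. When reading the results, quit attempts should be understood as those recorded in completed weekly surveys.

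### If the combined-PIF versus control contrast (about 2:1) is applied to a numeric outcome, pooled-variance tests risk miscalibrated p-values and confidence intervals; a separate-variance version costs almost nothing

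*Combined protocol and SAP*

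**What the plan says.** The Data Analysis section lists its methods in one sentence: Student t, "one-way ANOVA, ANOVA contrast tests, and Chi Square tests were used for analyses". It does not match tests to outcomes, and it mentions neither an unequal-variance version nor a check of the variances.

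Randomisation was to "either a) No-FIT control, b) PIF-ST, or c) PIF-DT", with stratification "resulting in slightly different sample sizes across condition". For intervention outcomes the plan states that "we focused our tests of significance on the PIF conditions combined compared to the no-FIT control". PIF-ST versus PIF-DT is a descriptive follow-up.

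Tolerability, one of the two primary outcomes, comes from 8 items "scored on a 1(strongly disagree) to 7(strongly agree) scale" and is reported in follow-up completers only. For it, the plan promises descriptive information and comparisons across conditions but names no contrast. Quit attempts are assessed in the weekly surveys; the text does not say whether they are analysed as yes/no or as a number. Retention, program completion, point prevalence abstinence and joint abstinence are yes/no.

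**The concern.** Student's t pools the variance by definition, and an ANOVA contrast does so by default because it uses the common error term. Pooling does little harm when groups are of similar size. It is not safe at about 1:2, because the larger group dominates the pooled estimate while the smaller group contributes most of the true sampling variance. If the smaller control group is the more variable one, the standard error is too small and the test rejects too often. If control is the less variable one, the standard error is too large and the test rejects too rarely.

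At stake is the calibration of the p-value and interval for any numeric outcome put through this contrast. A reader shown only the pooled result could not tell in which direction it errs.

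**Working it through.** **Inputs.** 95 targets in three arms of only slightly different size, described as "consistent with recommendations to recruit ~30 participants per treatment arm". I assume 32/32/31, so 32 control versus 63 PIF (1:1.97). For tolerability, retention at the 80% target gives 0.80 × 95 = 76 completers, assumed 26 versus 50. The two-sided 5% level and all SD ratios are assumptions.

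**The plan's own figure.** The plan says "an intent-to-treat sample of ~95 targets would allow us power of ~82% to compare the control and PIF conditions". It gives no outcome, effect size, alpha or sidedness, so the figure can only be solved backwards. With √(32 × 63 / 95) = 4.607, a standardised difference of 0.624 gives 0.624 × 4.607 − 1.96 = 0.91, which is 82% power two-sided. One-sided, the difference needed is 0.556. The figure can be neither confirmed nor refuted, and it says nothing about variances.

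**Large-sample check.** Let C be control and P be combined PIF.

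- True variance of the difference: V = σ_C²/n_C + σ_P²/n_P
- Variance the pooled test uses: V_p = [(n_C − 1)σ_C² + (n_P − 1)σ_P²]/(n_C + n_P − 2) × (1/n_C + 1/n_P)
- Actual type I error ≈ 2[1 − Φ(1.96 √(V_p/V))]

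For σ_C = 1.25 and σ_P = 1: V = 1.5625/32 + 1/63 = 0.0647. V_p = (31 × 1.5625 + 62)/93 × 0.04712 = 1.1875 × 0.04712 = 0.0560. The root of the ratio is 0.930, the effective cut-off is 1.823, and the error rate is 6.8%.

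**Simulation.** Normal data with equal means, 100,000 data sets per row (Monte Carlo standard error about 0.07 points at 5%). The contrast is (−1, ½, ½) over 32/32/31.

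| Control/PIF SD ratio | Formula | Student t, 32 v 63 | Pooled contrast | Student t, 26 v 50 |
|---|---|---|---|---|
| 1 | 5.0% | 5.0% | 5.0% | 5.0% |
| 1.25 | 6.8% | 6.8% | 6.7% | 6.8% |
| 1.5 | 8.5% | 8.3% | 8.3% | 8.5% |
| 2 | 10.9% | 10.9% | 10.8% | 10.8% |
| 0.8 | 3.5% | 3.6% | 3.6% | 3.5% |
| 0.67 | 2.6% | 2.7% | 2.7% | 2.8% |
| 0.5 | 1.7% | 1.8% | 1.8% | 1.9% |

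Welch's t and the separate-variance contrast stayed between 4.9% and 5.1% in every row.

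**A bounded score with different means.** Suppose the SD on the 1–7 scale is proportional to √(p(1 − p)), with p = (mean − 1)/6. A control mean of 5.5 and a PIF mean of 6.0 give p = 0.75 and 0.833, and a variance ratio of 0.1875/0.1389 = 1.35 (SD ratio 1.16). Then V = 1.35/32 + 1/63 = 0.0581 and V_p = 1.1167 × 0.04712 = 0.0526, so the pooled 95% interval misses about 6.2% of the time. With the means swapped it misses about 4.0%. Simulation of such a score gave 6.3% and 3.8%, against 5.1–5.2% for Welch.

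**Where the problem does not reach.** PIF-ST versus PIF-DT at an SD ratio of 2: Student 5.3%, Welch 4.9%. Three-arm omnibus ANOVA: 5.2–6.1% over the unequal-SD cases tried. Yes/no outcomes go to chi-square.

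**Skewed counts.** Negative binomial with mean 2 in both groups, 32 versus 63. With SD 3.16 in control and 2.00 in PIF, Student gives 9.0% and Welch 7.0%. With the SDs reversed, 3.4% and 4.9%.

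**Price of Welch.** With equal SDs and a standardised difference of 0.65, power falls from 84.3% to 84.0% (32 versus 63) and from 75.7% to 75.2% (26 versus 50).

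**The case against.** The strongest reply is that the natural reasons to expect unequal spread do not produce the type I errors in the table. On a bounded scale, or with a count whose variance rises with its mean, the variances differ because the means differ. Equal means then bring equal variances, and Student holds 5%. In a randomised comparison with no effect at all, the distributions are identical. This stands. For those mechanisms the damage falls on the confidence interval when means differ, and it is modest: about 6% or 4% non-coverage in the example above. The 8–11% figures need equal means with markedly unequal spread, which nothing in the documents suggests.

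A reader might infer that the error rate of a primary outcome is wrong. The documents do not support that. They give no SDs, they tie the combined-PIF contrast to intervention outcomes and not expressly to tolerability, and a comparison of tolerability over three near-equal arms would be little affected. Pooling is explicit only for Student's t; for the contrasts it is the default, and the text is silent.

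A reader might also infer that Welch cures every numeric outcome. Quit attempts are not defined as a count, and if they are a skewed count, Welch corrects only part of the error.

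What survives is that the plan names t and contrast tests, that its preferred comparison is about 1:2, and that a better-calibrated version is available at almost no cost.

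**Conclusion.** The point holds as a conditional, minor improvement. For a numeric outcome tested as combined PIF versus control, the pooled method is calibrated only if the spreads are similar, and the plan neither states nor checks this. At SD ratios of 1.25 and 0.8, the nominal 5% becomes just under 7% and about 3.6%. At 2 and 0.5, which should be read as extremes, it becomes about 11% and 1.8%.

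This rests on an assumed 32/63 split, assumed SD ratios, roughly normal data, and the contrast being used for tolerability or for quit attempts analysed as a number. It gives no reason to doubt the yes/no outcomes, PIF-ST versus PIF-DT or the omnibus ANOVA, and it does not show that any reported p-value is wrong.

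**What to change.** - State which test applies to which outcome, including the contrast used for tolerability and whether quit attempts are yes/no or a number.
- For numeric outcomes compared as combined PIF versus control, use Welch's t, or the same contrast with separate group variances (or HC3 standard errors). Report the mean difference with the matching 95% CI.
- If quit attempts are analysed as a skewed count, use a count model or a permutation test instead.
- The chi-square tests can stay, and changing the omnibus ANOVA would gain little.

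The cost is a wording change, a software option and a rerun of existing data (the text describes enrolment and follow-up as done). The loss is under 1 point of power if the variances are in fact equal.

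### Does testing the two PIF arms combined against control hide the effect of paying both partners on joint abstinence?

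*Combined protocol and SAP*

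**What the plan says.** The Baseline section describes the two incentive arms: "either the target (PIF-ST) or both members (PIF-DT) were offered compensation". Measures lists four secondary outcomes, the last being "Joint abstinence, defined as both couple members being abstinent at follow-up". Data Analysis reports outcomes separately for targets and partners, "with the exception of joint abstinence which was defined at the dyad-level".

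On contrasts, Data Analysis says four things:

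- Significance testing: "we focused our tests of significance on the PIF conditions combined compared to the no-FIT control".
- All analyses: "For each analysis, we provide descriptive information as well as comparisons across conditions".
- Between the PIF arms: "We provide descriptive follow-up tests comparing PIF-ST and PIF-DT", with a warning that these tests are imprecise and need cautious reading in a pilot.
- Partners: their results are treated as "outcomes as further descriptive dependent variables".

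Participants and Recruitment gives the power basis: "an intent-to-treat sample of ~95 targets would allow us power of ~82% to compare the control and PIF conditions".

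**The concern.** Targets receive the same offer in both PIF arms, so pooling the arms looks natural for target outcomes, and the power statement is about targets. Joint abstinence is different. A couple counts only if both members quit, and the arms differ in whether one or both of those members are paid. The pooled result is then a weighted average of a one-incentive and a two-incentive effect. If PIF-ST does less than PIF-DT, the average is smaller than the PIF-DT effect, and a reader might take a weak pooled result as evidence that paying both members does not work. The plan names the pooled contrast and PIF-ST versus PIF-DT, but does not name PIF-DT versus control or PIF-ST versus control.

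**Working it through.** **The plan's own figure.** The stated power of about 82% cannot be reproduced or refuted, because the outcome, rates, alpha and sidedness are not given. With 32 versus 63 (assumed, from 95 couples split about equally) and two-sided 5%, 82% corresponds, for example, to 5% versus 28.5% or 10% versus 36.4%. The figure concerns targets and makes no claim about joint abstinence.

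**How large could the averaging be?** All rates and arm sizes here are assumed: control/PIF-ST/PIF-DT 32/32/31, members quitting independently at 10% unpaid and 40% paid. Let s be the share of the paid–unpaid gap that the unpaid PIF-ST partner gains.

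- Control joint rate: 0.10 × 0.10 = 1%.
- PIF-DT joint rate: 0.40 × 0.40 = 16%, so its effect is 15 points.
- PIF-ST joint rate: 0.40 × (0.10 + 0.30s).
- Ratio = [(32 × PIF-ST + 31 × PIF-DT)/63 − control] / (PIF-DT − control).

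| s | PIF-ST | Pooled effect (points) | Ratio | Chi-square power, pooled | Chi-square power, PIF-DT vs control |
|---|---|---|---|---|---|
| 0 | 4% | 624/63 − 1 = 8.9 | 0.59 | 21% | 64% |
| 0.5 | 10% | 816/63 − 1 = 12.0 | 0.80 | 47% | 64% |
| 0.75 | 13% | 912/63 − 1 = 13.5 | 0.90 | 59% | 64% |
| 1 | 16% | 1008/63 − 1 = 15.0 | 1.00 | 69% | 64% |

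Powers are exact enumerations of the uncorrected chi-square test at two-sided 5%. The averaging is real arithmetic, but its size runs from large to nil depending on s, about which the documents say nothing. With weaker assumed rates (5% unpaid, 20% paid, within-couple correlation 0.3), pooled power is about 2.5% to 12% and PIF-DT versus control about 18%, so neither contrast would tell a reader much.

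**Is the arm-level information lost?** Let P be the pooled difference from control, F the PIF-DT minus PIF-ST difference, and w_ST and w_DT the arms' shares of the pooled PIF group. Then

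- PIF-DT − control = P + w_ST × F
- PIF-ST − control = P − w_DT × F

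Three arms have only two independent differences, and the plan names two. Take assumed joint counts of 0/32, 1/32 and 5/31:

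- P = 6/63 = 9.5 points; F = 16.1 − 3.1 = 13.0 points.
- PIF-DT − control = 9.52 + (32/63) × 13.00 = 16.1 points; directly, 5/31 = 16.1.
- PIF-ST − control = 9.52 − (31/63) × 13.00 = 3.1 points; directly, 1/32 = 3.1.

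**Can different patterns be told apart?** Take assumed arms of 31/32/32 with one jointly abstinent control couple.

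- PIF counts 1 and 8: P = 9/64 − 1/31 = 10.8 points; F = 8/32 − 1/32 = 21.9 points (95% Newcombe interval 4.6 to 39.2).
- PIF counts 4 and 4: P = 8/64 − 1/31 = 9.3 points; F = 0 (−17.3 to 17.3).

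The pooled results are similar, but the follow-up contrast that the plan already includes separates the two patterns.

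**Is the label missing?** The pooled test is described as the PIF conditions combined, and the Baseline section states who is paid in each arm. The averaging is on the face of the plan.

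**The case for a change.** The strongest counter-argument is that point differences are not inference. The follow-up contrast does not say whether either arm beats control, and intervals for the arm-level differences do not follow from P and F alone. With counts 0/32, 1/32 and 5/31, the pooled interval is −2.3 to 19.3 points and the PIF-DT versus PIF-ST interval is −2.5 to 29.7, while PIF-DT versus control is 2.1 to 32.6. Only the contrast that is not named excludes zero. At s = 0 the power gap, 21% against 64%, is not small.

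The arithmetic stands. It does not make the plan wrong. Those counts were chosen to produce the split; 4/32 in each PIF arm against 1/31 gives 9.3 points for the pooled and for each arm-level difference. At s = 1 the pooled test is the stronger one, 69% against 64%. An arm-versus-control contrast promoted because it crosses a threshold that the focused test misses would be a post hoc choice, with enrolment finished in May 2022, a document dated April 2024 and analysts not blind to condition. The plan's general undertaking to compare conditions does not exclude arm-versus-control comparisons, and given arm-level counts a reader can compute any such interval.

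Nor is the line between target outcomes and joint abstinence sharp. If a paid target can influence an unpaid partner, a paid partner can influence the target, so the pooled contrast may average unequal effects for targets too. That is a property of any pooled contrast, and here it is declared.

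For partners, the text does not say whether the pooled test is applied. Since their results are called descriptive, no conclusion of the plan depends on it.

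**Conclusion.** The concern does not hold. Followed as written, the plan gives a valid and openly labelled any-PIF versus none test for joint abstinence, with a descriptive comparison between the PIF arms, from which each arm's difference from control follows by subtraction. No number, rule or test needs correcting. How far the pooled effect falls below the PIF-DT effect is unknown: the ratio is 0.59 to 1.00 in the main illustration, on rates, spillover and arm sizes that are all assumed. The reach is one of four secondary outcomes, with about 32 couples per arm, in a pilot whose primary outcomes are feasibility and tolerability.

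The conclusion assumes that the descriptive information provided for each analysis includes joint abstinence by arm. Table 2 and Figure 2 are not in the available text, so this could not be confirmed, and arm-level results or intervals may already be there. Naming the arm-versus-control intervals would be a matter of reporting taste.
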